⁴Muscle Tissue Biopsies (Optional): A biopsy of the Vastus Lateralis muscle will be performed using the Bergstrom technique. Subjects will be placed in a supine position and the skin will be cleansed with chlorhexidine solution. After a sterile drape is placed over the skin, local anesthesia (1%-Lidocaine HCl) will be administered,. The skin will be incised (approximately 0.75 cm) with a #11 scalpel, and the Bergstrom needle will be inserted into the Vastus Lateralis. Up to 250mg of muscle tissue will be obtained under suction. After the biopsy, pressure will be applied to stop bleeding and the skin will be closed with Steri strips (suture(s) if allergy to steri strips). A sterile dressing will be applied. An MD, DO, NP, or PA will conduct this procedure. Collected tissue will be snap-frozen for future analyses.

⁵Hyperinsulinemic-euglycemic Clamp: Hyperinsulinemic-euglycemic clamp: The glucose clamp is the gold standard for measurement of insulin sensitivity and will be performed similarly to the procedure initially described by Defronzo in 1979. The overall concept of the euglycemic clamp is that insulin is infused to stimulate glucose uptake and inhibit endogenous glucose production, and the rate of 20% glucose infusion necessary to maintain euglycemia can be used to assess whole body insulin sensitivity.

After an overnight 10-hour fast, an intravenous catheter will be placed for infusion of insulin and glucose. A second catheter will be placed in a vein of the contra-lateral arm for blood withdrawal. After baseline blood is collected, a 2-step euglycemic clamp will be started with a 2-hour infusion of insulin (Humulin-R) at 10 mU/m²/min, followed by 2 hours at 40 mU /m²/min. Whole blood will be used to assess plasma glucose at 5-10 min intervals via NOVA StatStrip Glucose Meter or YSI. Plasma glucose will be allowed to either decrease to ~90 mg/dl or will be increased to ~90 mg/dl in each participant depending on the fasting blood glucose levels. Euglycemia (~90 mg/dL) will be maintained by measuring blood glucose at 5-10 min intervals via a NOVA glucometer or YSI and using a variable 20% dextrose infusion.

Throughout the clamp blood samples are collected at -30min, -20min, -10min, 0min, +45min, +90min, +100min, +110min, +120min, +180min, +220min, +230min, and +240min of insulin infusion. Total blood volume during this procedure will be approximately 260 mls.

Calculations:

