Insulin sensitivity (M/I) will be calculated using the formula: $M/I = R_d$ / (steady state insulin level - basal insulin level) where steady state insulin equals the average insulin concentration during the last 30-40 minutes of each steady state phase of the clamp.

Fasting and insulin-suppressed FFA [IS-FFA] will be measured as a measure of adipose tissue insulin sensitivity with an ultrasensitive FFA assay from Wako.

⁶Subcutaneous Microdialysis: To assess antilipolytic sensitivity of WAT to insulin and production of hormones, proteins, and other factors (including, but not limited to amyloid precursor protein (APP) TNF-a, leptin, and adiponectin), up to four microdialysis catheters will be inserted into the periumbilical subcutaneous adipose tissue. Topical anesthesia (EMLA cream) or ethyl chloride will be applied to each insertion site.

[figure not shown]
The catheters come as a sterilized kit (CMA Microdialysis) with a sterilized cutting needle (20-gauge) and introducer needle (54mm long X 1.4 mm diameter). The insertion site will be cleaned with chlorhexidine and a small incision made using the provided cutting needle. The catheter will be inserted using the introducer needle, which is then removed, and the catheter secured under a clear adhesive dressing. Flow to the microdialysis catheters will be initiated and dialysate collected in approximately 30-minute samples; the catheters will be calibrated using zero-net flow methods. Perfusate will consist of sterile 10 mM ethanol in ringers injection to account for changes in adipose tissue blood flow. The microdialysis collection will proceed during the glucose clamp. Approximately 66 mL of blood and less than 8 mL of interstitial microdialysate will be obtained.

The rates of carbohydrate and lipid oxidation will be calculated as described by Elia and Livesey. The basal rate will be calculated by averaging the data for the time= -20 to time=0 minutes (fasting RQ), and insulin-stimulated glucose and lipid oxidation rates will be calculated by averaging the data for the time=40 to time=60 minutes (post glucose administration RQ).

⁷Blood Draw: After the IV catheters are inserted and prior to the clamp procedures beginning, a baseline blood draw will be collected from the venous catheter. The following will be measured: CBC with differential and platelets, CMP, lipid profile, blood glucose, ALT, AST, alkaline phosphatase, insulin level, TSH, and HbA1C.

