⁸Respiratory Quotient (RQ): Indirect calorimetry will measure the respiratory quotient (RQ) and substrate utilization using either a ParvoMedics Metabolic Cart at TRI (Salt Lake City, UT) or Omnical Cart at PBRC (Maastricht Instruments BV). The ParvoMedics Metabolic Carts are calibrated daily before each subject with standardized gases containing

1% CO₂, 16% O₂ and balance N₂. The Omnical Carts are also calibrated daily before each subject with standardized gases containing 0.8% CO₂, 18% O₂ and balance N₂ and then self-calibrate continuously through the test approximately every 15 minutes. After inserting the clamp catheters, completing the WAT and muscle biopsies, and inserting the microdialysis catheters, and allowing flushing of the microdialysis catheters for 5 minutes, participants will rest for 60 minutes laying down in a Semi-Fowler's position. After 30 minutes of dialysate collection, a transparent plastic hood connected to the device will be placed over the head of the subject. Calculations of O₂ consumption (VO₂) and CO₂ production (VCO₂) will be made by comparing measures of the O₂ and CO₂ concentrations of the testing room (measured every 5 minutes at TRI and every 2 minutes at PBRC) to continuous measurements of O₂ and CO₂ concentrations in expired air diluted in a constant air flow (15-30 L/min at TRI and 85-90 L/min at PBRC) generated by a pump. From the above, energy expenditure standardized for temperature, pressure, and moisture will be calculated at one-minute intervals. After ~30 minutes, the remaining clamp procedures will resume. This will be repeated during steady state 1 (+90-120min) and steady state 2 (+210-240mins).

Standardized Meal and Accelerometer: After all procedures are complete, participants will be provided a standardized meal along with post procedure instructions. Participants will also be provided with a triaxial activity monitor (Actigraph GT3X) which will be worn for 7-10 days. The monitor integrates motion sensor data from the tri-axial accelerometer to estimate the energy cost of free-living activity. The participant will wear the monitor at

all times, except while showering or bathing. After the period of wear time, the participant will return the monitor and the data will be uploaded.

¹⁰7-Day Food Record (optional): Participants will be asked to record their food and beverage intake for 7 days and return the form to the research site at their next in-person visit.

Phone Follow-up After Baseline Visit 2

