- 3. Cellular composition of WAT. Cell composition and gene expressions in WAT will be assessed two times (pre and post exercise intervention) by snRNAseq on the frozen adipose tissue.
- 4. Adipocyte morphology, senescence, and inflammation. Adipocyte size, markers of cellular senescence and inflammation will be assessed two times (pre and post exercise intervention) by immunohistochemistry on the formalin-fixed paraffin-embedded adipose tissue.

Secondary outcomes:

1. Whole body and WAT-specific insulin resistance: Whole-body insulin resistance and WAT-specific antilipolytic sensitivity to insulin will be evaluated pre and post exercise intervention *in vivo* using blood and dialysate samples collected during glucose clamp and subcutaneous microdialysis.

Data Management and Quality Plan

Data De-identification

Participants will be enrolled and assigned a participant identification number (PID). This PID is a code consisting of a combination of numerals and letters, which serves as the identifier for this participant for this research study and links them back to their hospital medical record and their protected health information (PHI). Access to the "link" between the PIDs, the PHI, and to the clinical data are only granted to the clinical research team as assigned on the Delegation of Authority Log. All the clinical research and survey data is recorded in a de-identified fashion onto our paper source documents and/or electronic case report forms (CRF). Both sites will enter data into REDCap, a HIPAA-compliant, web-based forms and survey platform approved for use by AdventHealth. REDCap will be used for storage and to facilitate analysis. All data not entered into REDCap (e.g., data collected from individual exercise sessions) will be stored on a shared OneDrive folder only accessible to the assigned study-specific research team at PBRC and AH TRI.

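### The averaging window for insulin-stimulated oxidation (minutes 40 to 60) coincides with no scheduled calorimetry session

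*Protocol*

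**What the plan says.** All of this is in the protocol, under Study Visits, Baseline Period – Visit 2, and Visit 4 repeats the same procedures after the intervention.

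- **Item 5 (clamp).** "a 2-step euglycemic clamp will be started with a 2-hour infusion of insulin", and a second 2-hour step at a higher rate follows. The blood samples run from -30 minutes to "220min, +230min, and +240min of insulin infusion", so the clock counts from the start of insulin.
- **Item 6 (microdialysis; its last paragraph covers oxidation rates).** For the stimulated state, "insulin-stimulated glucose and lipid oxidation rates will be calculated by averaging the data for the time=40 to time=60 minutes (post glucose administration RQ"). The fasting value is the mean over minutes -20 to 0. No time origin is given for either window.
- **Item 8 (respiratory quotient).** The hood is first used for about 30 minutes before the clamp proceeds. Then: "This will be repeated during steady state 1 (+90-120min) and steady state 2 (+210-240mins"). On resolution, "energy expenditure standardized for temperature, pressure, and moisture will be calculated at one-minute intervals".
- **Study Outcome Measures, secondary outcomes.** "Whole-body insulin resistance and WAT-specific antilipolytic sensitivity to insulin will be evaluated pre and post exercise intervention". Carbohydrate and lipid oxidation are named in neither the primary nor the secondary list.

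**The concern.** Item 6 fixes explicit minutes for a calculation, and item 8 schedules no recording at those minutes. This is a stated rule that conflicts with the stated schedule, not a detail left for the statistical analysis plan.

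Two things follow. First, the rule cannot be carried out literally, so the analyst has to replace it. Second, it produces one stimulated value although there are two insulin steps, each with its own hood session. The steps run at 10 and 40 mU/m²/min, a fourfold difference, so the choice of step is part of the definition of the variable. The same rule governs the pre- and post-intervention measurements at two sites that use different metabolic carts. If it is settled after data are in hand, the choice could be influenced by the results, and the sites could read the rule differently.

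**Working it through.** This is a check of overlapping time intervals; no power or sample-size figure is involved.

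**Inputs**

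- Stimulated window: 40 to 60 minutes (item 6). Length 60 − 40 = 20 minutes, or 20 values if the oxidation data share the one-minute resolution that item 8 gives for energy expenditure.
- Basal window: -20 to 0 minutes (item 6). Length 0 − (-20) = 20 minutes.
- Hood sessions (item 8): about 30 minutes before the clamp, taken here as about -30 to 0; +90 to +120; +210 to +240.
- Clamp steps (item 5): 0 to 120 and 120 to 240 minutes of insulin infusion.
- Steady state for the insulin average (item 6, or the calculations just before it): the last 30 to 40 minutes of each phase, which is from +80 or +90 to +120 and from +200 or +210 to +240.

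**Formula.** For windows [a, b] and [c, d], overlap = max(0, min(b, d) − max(a, c)).

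**Basal window first.** [-20, 0] with [-30, 0]: min(0, 0) − max(-20, -30) = 0 − (-20) = 20 minutes. The basal rule can be applied in full.

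**Stimulated window on the insulin-infusion clock**

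| Hood session | min(b, d) − max(a, c) | Overlap |
|---|---|---|
| about -30 to 0 | 0 − 40 = -40 | 0 min |
| +90 to +120 | 60 − 90 = -30 | 0 min |
| +210 to +240 | 60 − 210 = -150 | 0 min |

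So 0 of 20 one-minute values are scheduled. The window ends 30 minutes before the first on-insulin session and 150 minutes before the second. It also ends 20 to 30 minutes before the protocol's own steady state in step 1 begins (80 − 60 = 20; 90 − 60 = 30).

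**Other possible time origins**, since item 6 names none:

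- *Start of each clamp step.* The window becomes +40 to +60 and (120 + 40) to (120 + 60) = +160 to +180. The second gives 180 − 210 = -30 against the last session. No overlap in either step.
- *Start of each hood session.* Each session lasts about 30 minutes, so minute 40 does not exist.
- *Start of the 60-minute pre-clamp rest.* If dialysate collection starts with the rest, the hood is on from about minute 30 to 60, and 40 to 60 lies inside it. No insulin is running then, so the values cannot be insulin-stimulated.
- *Start of dextrose.* Item 5 fixes no start time, because glucose is first brought to about 90 mg/dl. With dextrose starting at s, the window s + 40 to s + 60 lies inside +90 to +120 only if s is between 50 and 60, and inside +210 to +240 only if s is between 170 and 180. It would differ by participant.
- *Cumulative hood minutes after the basal session.* The first on-insulin session occupies 0 to 30 and the second 30 to 60. Then 40 to 60 maps to 210 + (40 − 30) = +220 through 210 + (60 − 30) = +240.

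Only the last reading yields insulin-stimulated data by a fixed rule. The protocol text does not state that clock, and it would leave the steady state 1 recording without a use in this calculation.

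**The case against.** The strongest reply is that item 6 never says its minutes are minutes of insulin infusion. The basal window fits equally well as the last 20 minutes of a 30-minute hood recording, and on a cumulative hood clock the stimulated window would be the last 20 minutes of the steady state 2 session. That reading is symmetrical and would make a single stimulated value deliberate. A figure in item 6 is also missing from the text at hand, so its content could not be checked.

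What stands: the time origin is undefined, and the cumulative reading may be what was meant. It does not rescue the rule, because a reader cannot get there from the text. The only clock the protocol states is the insulin-infusion clock, item 8 itself labels its sessions on that clock, and the cumulative reading ignores a session that item 8 schedules.

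Two further points are fair. The effect is small, because no listed outcome depends on this window and the recordings exist. And the label about glucose administration is not false, since dextrose does run during the clamp; it simply fixes no time. The choice of the last 20 minutes over a full 30-minute session is also open to the sponsor.

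**Conclusion.** The point holds. On the protocol's stated clock the averaging rule covers 0 of the 20 minutes it names, and of the alternative origins examined only an unstated cumulative hood clock gives a fixed, usable window. The rule also leaves open which of the two insulin steps the stimulated rate describes.

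The consequence is confined to the insulin-stimulated glucose and lipid oxidation rates. The basal rates, M/I, free fatty acid suppression, microdialysis and the sample size do not use this window, and no data are lost because both steady states are recorded. It should be corrected before analysis, but it does not threaten the trial's main conclusions.

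The conclusion assumes that the pre-clamp session ends at about the start of insulin (item 8 gives its length but no clock time) and that the missing figure does not define a different clock.

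**What to change.** Reconcile items 6 and 8 of the Baseline Visit 2 procedures, which will also cover Visit 4:

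1. State the time origin for the oxidation windows.
2. State whether rates are reported for one insulin step or both, and name the step if only one is meant.
3. Place the stimulated window inside a scheduled hood session, preferably with the same 20-minute length as the basal window.
4. Drop the label about glucose administration, or replace it with the name of the clamp step.

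Wording that would do this, as an example:

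> Times are minutes of insulin infusion. Basal rates are averaged over -20 to 0. Insulin-stimulated rates are averaged over the last 20 minutes of each hood session (+100 to +120 for steady state 1, +220 to +240 for steady state 2) and reported separately by step.

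These windows follow from 120 − 20 = 100 and 240 − 20 = 220, and they coincide with blood samples already scheduled at +100, +110, +120 and at +220, +230, +240. Averaging over the full 30-minute sessions would also be consistent with the protocol if the sponsor prefers it, provided it is fixed in advance.

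The cost is one or two sentences. The hood schedule, the clamp and the burden on participants do not change.

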The participant will be contacted by phone within 24-72 hours after baseline visit 2 discharge to ensure no adverse events have occurred on both biopsy and arterial line sites.

Intervention Period (Weeks 1-12)

Biopsy and catheter insertion site check: A biopsy site and catheter site check will be done when the participants pick up their first supply of ${}^{2}H_{2}O$.

H₂O Administration and Return (12-week labelling period) and Urine Collections: ²H₂O will be prepared by the Mass Spectrometry Core. Participants will receive 50 mL aliquots of 70% ²H₂O or 35 mL aliquots of 99.9% ²H₂O in individual amber prescription containers. Participants will drink three 35 mL or 50 mL doses per day for the first week, and two doses per day from the second through the twelfth week. Participants will receive the ²H₂O aliquots containers bi-weekly, a log sheet to record consumption, and at-home urine collection cups with instructions. Participants will be instructed to keep urine samples taken at home in the refrigerator until their next in-person visit (every other week). Urine samples will be used to verify compliance weekly (at AH TRI or PBRC). Compliance with ²H₂O intake for both groups will be monitored through the weekly urine collections and return of empty containers for counting. ²H enrichments in urine, reflecting ²H body water enrichments, will be measured by isotope ratio mass spectrometry. Enrichments are expected to be between 1-2.5%. If a participant's urine sample is <1%, the study team will encourage compliance with the participant. If enrichment is <1% for a period of 3 weeks, the PIs will discuss participant withdrawal. Participants will be instructed to maintain their normal daily and weekly routines.

Participants in the EX group will engage in 12-week endurance exercise training.

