Endurance Exercise Training: Outpatient. Approximate visit time: ~ 1.5 hour Participants in the EX group will engage in endurance exercise training three times a week for approximately 12 weeks. The exercise program will be supervised by a certified exercise physiologist and will take place at the TRI exercise training facility or at PBRC. Each session will last approximately 75 minutes with a 50-60 minute stimulus phase and the remaining time being used to warm up and cool down. Participants will use a cycle ergometer and/or treadmill for the duration of the intervention period. During all sessions, heart rate will be monitored using Zephyr heart rate monitors to ensure that participants maintain the target exercise intensity during training. Intensity will be set as a percentage

of heart rate reserve (calculated from pre-training VO_{2max}) and will increase during the intervention: $60\% \pm 5$ bpm for weeks 1-4; $70\% \pm 5$ bpm for weeks 5-8; $75\% \pm 5$ bpm for weeks 9-10; and $80\% \pm 5$ bpm for weeks 11-12. Self-reported perceptual data will be recorded periodically during exercise sessions and will be used to track the subjective experience of participants and in interpreting adherence data.

Body Weight Management and Health Education: All participants will be expected to maintain weight within ±2kg throughout the study. Should a participant gain or lose weight >2kg, the study team will be instructed on how to reduce or increase caloric intake to maintain body weight (Appendix). Participants in the EX group will be weighed onsite weekly and the study team will advise on weight maintenance, if needed. Participants in the CTRL group will be weighed onsite biweekly when they return and pick up ²H₂O. During biweekly on-site weigh ins, CTRL participants will be instructed on weight maintenance, if needed. Additionally, the study team will review the participant's physical activity habits and dietary habits, adverse events, and medication/medical history changes.

DEXA (Weeks 4-6): In addition to the pre- and post-intervention MRI and DEXA scans, during Weeks 4-6, one DEXA scan will be performed as described above to confirm maintenance of fat mass.

Review of Adverse Events: Study staff will assess for any adverse events at each exercise visit.

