Deuterium-labeled water (²H₂O) administration: ²H₂O-labeled water is water that is labeled with the stable, non-radioactive isotope deuterium. Deuterium-labeled water poses minimal health risk associated with drinking it. Participants may rarely experience transient dizziness or nausea following the initial intake.

Hyperinsulinemic-euglycemic clamp: There is the risk of bruising at the site of needle insertion in the veins. The risk of receiving an insulin infusion is that it could produce hypoglycemia (rare). Hypoglycemia may cause one to feel nervous, shaky, sweaty, hungry, and dizzy and have a rapid heart rate. If severe, hypoglycemia can cause coma, seizure or even death (all rare).

Current Version Date: 08/05/2024 IRBNet #: 1805407
Page 31 of 42

Resting Metabolic Rate/Respiratory Quotient (RMR/RQ): There is no physical risk associated with RMR/RQ. Other risks include a feeling of claustrophobia experienced by some subjects while under the transparent "hood".

Surveys: There are no risks involved beyond what would reasonably be encountered in everyday life. It is possible that participants may experience the following during completion of surveys:

- 1. Loss of privacy as a result of a breach of confidentiality
- 2. Undue stress related to content on the survey instruments

Mitigation of Risks

Dual Energy X-ray Absorptiometry (DEXA): A urine pregnancy test will be done prior to scans of all women of childbearing potential (all women except those with prior hysterectomy, tubal ligation, or absence of menses for ≥ 2 years).

Magnetic Resonance Imaging: There will be a strict safety screening protocol, to ensure any people with contraindications are excluded from volunteering.

Incidental Findings: There will be no diagnostic analysis associated with any of the MR sequences used in this protocol. However some of the MR images we obtain as part of this protocol may show incidental medical findings. In the case where a medical abnormality is apparent on an image, the image will first be reviewed by an investigator on this protocol. If the abnormality is confirmed, then the participant will be instructed to seek medical attention from their health care provider.

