- Administrative reasons require the participant's withdrawal;
- Participant is unable to complete a procedure;
- We are unable to place a venous line or place a catheter for the subcutaneous microdialysis.

Subject Request for Withdrawal from Study

Participation in this study is voluntary. Participants may decide not to participate in this study or may withdraw from this study at any time without penalty or loss of benefits. If a participant leaves the study before the final regularly scheduled visit, she/he may be asked by the study doctor to make a final visit for some 'end-of-study' procedures. This is to make sure that there are no safety concerns

Data Collection and Follow-up for Withdrawn Subjects

Participants who request withdrawal or who are withdrawn by the PI from the study will have their data maintained in the research database up to the point of withdrawal. The available data will be included in subsequent analysis because keeping these participants in the analysis is essential for study validity.

Adverse Events - Recording and Reporting

Each participant will be evaluated for adverse events at every study visit. Any event that is reported to the study staff and which meets the criteria of an adverse event will be documented as such and graded as to its attribution (unrelated to protocol, or possibly, probably, or definitely related to protocol) and severity (mild, moderate, or severe). Any severe and/or unanticipated adverse event will be immediately reported to the IRB according to AdventHealth IRB guidelines.

At each contact with the subject, the study team will seek information on adverse events by specific questioning and, as appropriate, by the Provider through examination. Information on all adverse events will be recorded immediately in the source document, also in the appropriate adverse event module of the case report form CRF. All clearly related signs, symptoms, and abnormal diagnostic procedures results

will be recorded in the source document. All adverse and unexpected events will be reported according to AdventHealth IRB guidelines.

Safety Monitoring Plan

Safety Monitoring

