Appendix:

The following table identifies the procedures in relation to the study timeline for CTRL group:

	Screen	В	aseline						² H:	2O Inter	vention	Period					F	Follow-	-up	
					Week															
Visits	SV1	V1	V	2	1	2	3	4	5	6	7	8	9	10	11	12	V3	V	4 §	
Days		-14	-8	-7	0-6	7-13	14-20	21-27	28-34	35-41	42-48	49-55	56-62	63-69	70-76	77-83	85	87	88	
Windows	Within 28 days of V1	±2	±2		±1	±1	±1	±1	±1	±1	±1	±1	±1	±1	±1	±1	±1	±1		
Informed Consent	X																			
Eligibility Assessment	X																			
Randomization		X																		
Urine Collection (urea, nitrogen and creatinine)			X															X		
Urine Collection (pregnancy, if applicable)	X	X							X								X			
Urine Collection (toxicology)	X																			
Physical Exam + Medical History	X																			
Vital Signs	X																			
Anthropometrics	X	X															X			
Screening Blood Draw	X																			
Electrocardiogram	X																			
Surveys			X															X		
MRI		X															X			
DEXA		X							X*								X			
VO2max Test		X															X			
Overnight Stay with Standardized Meal			X															X		
7-Day Food Record Start				X												X				
7-Day Food Record Return					X												X			
Hair Collection			X															X		
WAT Biopsy				X															X	
Muscle Biopsy				X															X	
Respiratory Quotient (Hood)				X															X	
Pre-Clamp Blood Draw				X															X	

Hyperinsulinemic-euglycemic Clamp + Microdialysis				X															X
Accelerometer Provided			X													X			
Biopsy and Catheter Insertion Site Check					X														X
On-site Body Weight Measurement							X		X		X		X		X				
Weight Maintenance and Health Education							X		X		X		X		X				
² H ₂ O Pick-up					X		X		X		X		X		X				
² H ₂ O Container Return							X		X		X		X		X	X			
² H ₂ O Urine Collection					X	X	X	X	X	X	X	X	X	X	X	X			
Review Adverse Events	X	X	X	X	X	X	X	X	X	X	X	X	X	X	X	X	X	X	X

^{*}DEXA can take place between Weeks 4-6 to increase scheduling flexibility

On-site Body Weight Measurement, Weight Maintenance and Health Education, and ²H₂O activities must occur on the first day of exercise for that week.

[§]Visit 4 procedures must be done within 36-48 hours after the VO2max test

The following table identifies the procedures in relation to the study timeline for EX group:

The following table identifi	Screen		Baseline						H ₂ O and		_	ention P	eriod				Fo	llow-u	-up
			Week																
Visits	SV1	V1	V	2	1	2	3	4	5	6	7	8	9	10	11	12	V3§	V	7 4

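### As written, adverse events are asked about some 36 times in EX and 7 to 8 times in CTRL during Weeks 1-12, although both schedules mark a weekly review

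*Protocol*

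**What the plan says.** All references are to the Protocol.

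- **Intervention Period, Review of Adverse Events:** "Study staff will assess for any adverse events at each exercise visit".
- **Intervention Period, Endurance Exercise Training:** "Participants in the EX group will engage in endurance exercise training three times a week for approximately 12 weeks". CTRL has no exercise visits.
- **Intervention Period, Body Weight Management and Health Education:** "Participants in the CTRL group will be weighed onsite biweekly when they return and pick up" their labelled water. Shortly after: "Additionally, the study team will review the participant's physical activity habits and dietary habits, adverse events, and medication/medical history changes". No interval other than the biweekly one is given for CTRL.
- **Adverse Events - Recording and Reporting:** "Each participant will be evaluated for adverse events at every study visit". The same section requires specific questioning at each contact.
- **Appendix, schedules for CTRL and EX:** the row "Review Adverse Events" is marked in every one of Weeks 1 to 12 in both tables.
- **Phone follow-up:** calls are described only after Visit 2 and after Visit 4, none in Weeks 1-12.
- **Potential Risks, deuterium-labelled water:** "Participants may rarely experience transient dizziness or nausea following the initial intake". Both arms drink it, and the number of daily doses is highest in the first week.

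**The concern.** How often an arm is asked about adverse events should not depend on which arm it is. Here the text lets the number of prompts follow the number of visits, and visits differ sharply between EX and CTRL. The schedules imply something else, a weekly review in both arms, but the text gives no means of carrying it out in CTRL in the even-numbered weeks.

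Two things are at stake. First, an excess of mild events in EX could not be told apart from the effect of asking more often. Second, CTRL is the only arm that receives labelled water without exercise, so it is the cleanest source of information on that exposure. It is not asked during the first two weeks of intake, the period in which the named reaction would be expected.

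**Working it through.** There is no stated figure to reproduce. The check is a count of contacts in Weeks 1-12.

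**EX.** 3 sessions per week × 12 weeks = 36 prompts.

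**CTRL**, from the rows of its schedule:

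| Row | Weeks marked |
|---|---|
| Labelled-water pick-up | 1, 3, 5, 7, 9, 11 |
| Container return | 3, 5, 7, 9, 11, 12 |
| On-site body weight | 3, 5, 7, 9, 11 |
| DEXA | 5, allowed anywhere in Weeks 4-6 |
| Labelled-water urine sample | 1 to 12 (home samples, brought to the next visit) |
| Adverse event review | 1 to 12 |

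The weeks with an on-site activity are 1, 3, 5, 7, 9, 11 and 12, which makes 7. A DEXA on a separate day makes 8. This takes the Week 12 return as an in-person contact.

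**Ratios, EX to CTRL**

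- 36 / 7 = 5.1
- 36 / 8 = 4.5
- If CTRL were somehow reviewed weekly while the EX text stood: 36 / 12 = 3.0
- If one weekly review were done in both arms: 12 / 12 = 1.0

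**Weeks marked for review without a routine CTRL contact.** 2, 4, 6, 8 and 10. The DEXA may cover Week 4 or Week 6, but not both.

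**Start of labelled water.** CTRL collects the first supply in Week 1 (days 0-6) and is next due in Week 3 (days 14-20), about 14 days later. No prompt is described in between. EX has three sessions in each of Weeks 1 and 2. The EX schedule puts labelled-water activities on the first exercise day of the week, so 2 + 3 = 5 sessions follow the pick-up before Week 3 begins. The comparison over that interval is 5 prompts against none. It assumes that CTRL participants start drinking after leaving the pick-up visit. The protocol does not say whether the first dose is taken on site.

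**Do the general rules close the gap?** No. Questioning at every visit and every contact applies to both arms, but it multiplies whatever contacts exist. It adds none in CTRL.

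**The case against.** The best case against runs as follows. The sentence on exercise visits is not the whole rule: the weigh-in paragraph and the adverse event section require active questioning of CTRL too. The schedules already show that weekly review is intended, so this is a mismatch between text and table rather than a poor design. More contact is inherent in supervised training, and asking at each session suits an intervention with risks during the session. No safety outcome is listed, no by-arm adverse event analysis is stated, and events are graded individually for attribution and severity.

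Much of this stands. CTRL is not left out of adverse event review, and it is not confined to the pick-ups, because the Week 12 return and a separate DEXA visit also count. Asking at every exercise session is reasonable and should continue. What does not follow is that solicited questioning has to be unequal: the extra sessions are inherent, but the lack of a common prompt is not. The intended weekly review also cannot happen in CTRL in weeks without a contact.

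A reader might go further and infer that exercise will be shown as more harmful than it is, by a definite amount. For example, if EX captured 90% of mild events and CTRL 50% to 80%, equal true rates would appear as a ratio of 0.90 / 0.80 = 1.1 to 0.90 / 0.50 = 1.8. The protocol gives no capture rates, and a 5:1 ratio of prompts does not translate into any particular ratio of recorded events. The protocol also describes the labelled-water risk as minimal and its symptoms as rare and transient.

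**Conclusion.** The point holds as a contradiction between text and schedule that produces unequal ascertainment. Followed as written, the protocol prompts EX about 4.5 to 5 times as often as CTRL in Weeks 1-12. It leaves CTRL unprompted from the Week 1 pick-up to Week 3, and it marks CTRL reviews in up to five weeks with no described contact at which to do them. These counts rest on full attendance at three sessions a week for 12 weeks and on the contacts that the CTRL schedule shows.

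The consequence is limited. Adverse event counts by arm would not be comparable, whether in the safety committee's review of events or in a later report, and mild labelled-water reactions in CTRL would depend on recall or on participants volunteering them. The direction, more complete recording in EX, is plausible, but its size cannot be derived from the document. The primary endpoint is not touched, and no planned test is biased, because no between-arm adverse event test is stated. It should be corrected early, since mild events that were never asked about cannot be recovered later.

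**What to change.** Reconcile the intervention-period text with the schedules:

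- Use one standard adverse event question set, once a week in both arms, asking about the whole preceding week.
- In EX, ask it at the first session of each week.
- In CTRL, ask it at the biweekly pick-up and the Week 12 return, and by phone or REDCap form in weeks without a visit. The Week 2 contact then covers the start of labelled water.
- Keep recording and acting on every event raised at other exercise sessions, and carry it into that week's standard review so that it is not lost from the common record.
- Record how each event was elicited. Any by-arm table can then be read with and without events found only through the additional exercise-session contact. Counting only events raised at the common prompt would be unsafe, because an EX event mentioned mid-week might not be repeated, and the imbalance could then reverse.

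With 70 participants randomised 1:1, CTRL has 35. The cost is up to 5 contacts each, 35 × 5 = 175 in total, or 35 × 4 = 140 if every DEXA visit falls in Week 4 or 6 and serves as that week's contact. Beyond that it needs a wording change and some coordinator time. REDCap is already in use.
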